3.2.1 Safety

The primary safety analysis is the incidence of serious adverse events (SAE) of interest through 12 months defined as the following:

- Death
- COPD exacerbation, as defined as an acute worsening in respiratory symptoms requiring additional therapy, that requires a hospital stay of greater than 24 hours
- Pneumothorax within 2 days of either Gala Treatment procedure
- Pneumonia within 7 days of either Gala Treatment procedure, as defined as an increase in respiratory symptoms, fever, sputum production and or purulence with radiographic confirmation
- Respiratory Failure as defined as a requirement for mechanical ventilatory support for > 24 hours
- Arrhythmia requiring intervention or sustained (≥ 30 seconds) ventricular tachycardia

In addition to the primary safety analysis, additional pre-specified safety analyses will be performed in order to assess the totality of the safety profile of RheOx. Other, prespecified safety analyses include the incidence of treatment emergent adverse events (AE) and SAEs and an analysis of COPD exacerbations by severity.

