4 STATISTICAL METHODOLOGY

4.1 Sample Size Determination

Since this is an early feasibility study, no formal sample size calculations were conducted. Up to 30 patients will be enrolled and treated with the study device to assess the effect of the investigational device in the target population. This sample size was based upon clinical judgement rather than statistical considerations.

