4.8.2 Adverse Events

All reported AEs will be coded and classified by system organ class and lower level term (LLT) using the Medical Dictionary for Regulatory Activities (MedDRA).

The relationship to the device and/or procedure, system organ class, lower level term (LLT), and verbatim text for all adverse events will be listed. All treatment emergent AEs and SAEs will be summarized by the system organ class, LLT, and time interval. Device and/or procedure related adverse events will be summarized in a similar manner.

The following time intervals will be used:

- Treatment Emergent: Any event that occurred the day of or following Bronchial Rheoplasty 1 procedure through end of study.
- Treatment Recovery Period: Any event occurring the day of Bronchial Rheoplasty 1 procedure through 30 days following Bronchial Rheoplasty 2 procedure.
- 3 Months: Any event occurring during follow-up period through 90 days after Bronchial Rheoplasty 2, excluding treatment recovery period.

CONFIDENTIAL:

This document and its contents are the property of Gala Therapeutics, Inc. Any use, reproduction or distribution without the written permission of Gala Therapeutics, Inc. is prohibited.

	TYPE: Clinical Trial Document	Document No:	CLN-0000X
	TITLE: CS003 Statistical Analysis Plan	Revision:	A
		Release Date:	
		DCN	Page 9 of 44

- 6 Months: Any event occurring during the follow-up period between 91 days and 180 days after Bronchial Rheoplasty 2.
- 12 Months: Any event occurring during the follow-up period between 181 days and 365 days after Bronchial Rheoplasty 2.
- 2 Years: Any event occurring during the follow-up period between 366 days after Bronchial Rheoplasty 2 and 730 days after Bronchial Rheoplasty 2.
- 3 Years: Any event occurring during the follow-up period between 731 days and 1095 days after Bronchial Rheoplasty 2.
- 4 Years: Any event occurring during the follow-up period between 1096 days and 1460 days after Bronchial Rheoplasty 2.
- 5 Years: Any event occurring during the follow-up period between 1461 days and study completion.

SAEs and/or AEs leading to the discontinuation of study will also be listed.

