6 LIST OF TABLES

No.	Title	Population
14.1.1	Patient Disposition	All Patients
14.1.2	Patient Follow-up Status	All patients
14.1.3	Patient Enrollment and Disposition by Site	All patients
14.1.4	Protocol Deviations	Evaluable
14.1.5	Demographic and Baseline Characteristics	Evaluable
14.2.1	Procedure Results	Evaluable
14.2.2	Concomitant Medications through 12 Months	Evaluable
14.2.3	Concomitant Medications Post 12 Months	Evaluable
14.2.4	Quality of Life Outcomes through 12 Months	Evaluable
14.2.5	Quality of Life Outcomes Post 12 Months	Evaluable
14.2.6	HRCT Scan Quantitative Analysis	Evaluable
14.2.7	Pulmonary Function Testing through 12 Months	Evaluable
14.2.8	Pulmonary Function Testing Post 12 Months	Evaluable
14.2.9	Responder Analyses	Evaluable
14.3.1	Serious Adverse Events of Interest and Hospitalizations	Evaluable
14.3.2	High Level Summary of Non-Serious Adverse Events	Evaluable
14.3.3	High Level Summary of Serious Adverse Events	Evaluable
14.3.4	Non-Serious Adverse Event Summary through 12 Months	Evaluable

CONFIDENTIAL:

This document and its contents are the property of Gala Therapeutics, Inc. Any use, reproduction or distribution without the written permission of Gala Therapeutics, Inc. is prohibited.

	TYPE: Clinical Trial Document	Document No:	CLN-0000X
	TITLE: CS003 Statistical Analysis Plan	Revision:	A
		Release Date:	
		DCN	Page 14 of 44

No.	Title	Population
14.3.5	Non-Serious Adverse Event Summary Post 12 Months	Evaluable
14.3.6	Serious Adverse Event Summary through 12 Months	Evaluable
14.3.7	Serious Adverse Event Summary Post 12 Months	Evaluable
14.3.8	COPD Exacerbation Rates	Evaluable

CONFIDENTIAL:

This document and its contents are the property of Gala Therapeutics, Inc. Any use, reproduction or distribution without the written permission of Gala Therapeutics, Inc. is prohibited

	TYPE: Clinical Trial Document	Document No:	CLN-0000X
	TITLE: CS003 Statistical Analysis Plan	Revision:	A
		Release Date:	
		DCN	Page 15 of 44

Table #14.1.1 Patient Disposition

All Patients

Patient Status

Number of patients consented	xx
Excluded	xx/xx (xx.x%)
In Screening	xx
Enrolled (Treated)	xx/xx (xx.x%)
In Follow-up	xx/xx (xx.x%)
Completed Study	xx
Exited Study	xx
Withdrawn by Investigator	xx
Subject Withdrew Consent	xx
Death	xx
AE / SAE (other than death)	xx
Lost to Follow-up	xx
Other	xx

CONFIDENTIAL:

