Relationship/ Adverse Event	Treatment Recovery Period		3 Months		6 Months		12 Months		Total Events through 12 Months	
	n (%) [event] [1] (N)		n (%) [event] [2] (N)		n (%) [event] [3] (N)		n (%) [event] [4] (N)		n (%) [event] [5] (N)	
Number of TEAEs	xx		xx		xx		xx		xx	
Number of Subjects with any TEAEs	xx (xx.x%) [xx]	xx	xx (xx.x%) [xx]	xx	xx (xx.x%) [xx]	xx	xx (xx.x%) [xx]	xx	xx (xx.x%) [xx]	xx
Number of Subjects	xx		xx		xx		xx		xx	
All Adverse Events	xx (xx.x%) [xx]	xx	xx (xx.x%) [xx]	xx	xx (xx.x%) [xx]	xx	xx (xx.x%) [xx]	xx	xx (xx.x%) [xx]	xx
SOC	xx (xx.x%) [xx]	xx	xx (xx.x%) [xx]	xx	xx (xx.x%) [xx]	xx	xx (xx.x%) [xx]	xx	xx (xx.x%) [xx]	xx
LLT	xx (xx.x%) [xx]	xx	xx (xx.x%) [xx]	xx	xx (xx.x%) [xx]	xx	xx (xx.x%) [xx]	xx	xx (xx.x%) [xx]	xx
LLT	xx (xx.x%) [xx]	xx	xx (xx.x%) [xx]	xx	xx (xx.x%) [xx]	xx	xx (xx.x%) [xx]	xx	xx (xx.x%) [xx]	xx
Device-Related Only [6]	xx (xx.x%) [xx]	xx	xx (xx.x%) [xx]	xx	xx (xx.x%) [xx]	xx	xx (xx.x%) [xx]	xx	xx (xx.x%) [xx]	xx
SOC										
LLT										
LLT										
Procedure-Related Only [6]										
SOC										
LLT										
LLT										
Device-Related and Procedure-Related [6]										
SOC										
LLT										
LLT										

[1] Any event occurring after Bronchial Rheoplasty 1 procedure through 30 days following Bronchial Rheoplasty 2 procedure.

[2] Follow-up period through 3 months after Bronchial Rheoplasty 2, excluding either treatment recovery period.

[3] Follow-up period between 3 months and 6 months after Bronchial Rheoplasty 2.

[4] Follow-up period between 6 months and 12 months after Bronchial Rheoplasty 2.

[5] All treatment-emergent events occurring after Bronchial Rheoplasty 1 procedure through 12 months after Bronchial Rheoplasty 2.

[6] Events are considered device-related or procedure-related if judged by the treating investigator to be possibly, probably or definitely related to the device or procedure, respectively.

CONFIDENTIAL:

	TYPE: Clinical Trial Document	Document No:	CLN-0000X
	TITLE: CS003 Statistical Analysis Plan	Revision:	A
		Release Date:	
	DCN	Page 36 of 44	

Table # 14.3.5 Non-Serious Adverse Event Summary Post 12 Months

Evaluable Population

Relationship/ Adverse Event	2 Years [1]		3 Years [2]		4 Years [3]		5 Years [4]		Post-12 Months Total [5]	
	n (%)	[events] N	n (%)	[events] N	n (%)	[events] N	n (%)	[events] N	n (%)	[events] N
Number of TEAEs	xx		xx		xx		xx		xx	
Number of Subjects with any TEAEs	xx (xx.x%)	[xx]	xx (xx.x%)	[xx]	xx (xx.x%)	[xx]	xx (xx.x%)	[xx]	xx (xx.x%)	[xx]

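### The adverse event tables never give the number of patients with any treatment-emergent AE, or, by term, with any device-related AE, although the SAP text prespecifies both summaries

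*SAP*

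**What the plan says.** SAP 3.2.1 sets out safety analyses beyond the primary one: "Other, prespecified safety analyses include the incidence of treatment emergent adverse events (AE) and SAEs". SAP 4.8.2 adds: "All treatment emergent AEs and SAEs will be summarized by the system organ class, LLT, and time interval". It then says that AEs related to the device and/or procedure will be handled the same way. In SAP 4.8.1, incidence is reported as the count and percent of patients.

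The list of tables and the shells in SAP section 6 divide this up:

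- **Seriousness.** Tables 14.3.2, 14.3.4 and 14.3.5 are titled non-serious; Table 14.3.4, for example, is "Non-Serious Adverse Event Summary through 12 Months". Tables 14.3.3, 14.3.6 and 14.3.7 are titled serious. None combines the two.
- **Overall row.** Non-serious Tables 14.3.4 and 14.3.5 carry the row "Number of Subjects with any TEAEs". Serious Table 14.3.6 has the parallel row for TESAEs, but serious Table 14.3.7 goes back to the TEAE label.
- **Relatedness by term.** The four by-term tables (14.3.4 to 14.3.7) have three exclusive blocks: device-related only, procedure-related only, and both.
- **Relatedness overall.** Tables 14.3.2 and 14.3.3 show relationship to device and relationship to procedure separately, without terms or intervals, through 12 months, and within one seriousness class each.
- **Selected events.** Table 14.3.1 covers SAEs of interest and hospitalizations. Table 14.3.8 covers COPD exacerbations as rates per patient-year, with a row that pools all of them.

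**The concern.** The primary objective is safety. Two ordinary safety figures are how many patients had any AE, and how many had a given kind of AE attributed to the device. A reader of the planned tables gets neither as a patient count.

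The missing any-TEAE count also comes with a misleading label. A row that reads as overall TEAE incidence sits under a non-serious title. Programmed as titled, it leaves out any patient whose only events were serious.

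For relatedness, an event attributed to both device and procedure goes in a separate block. The device-only block therefore cannot be read as device-related incidence for that term, and adding the two blocks may count a patient twice.

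**Working it through.** There is no figure in the plan to reproduce: SAP 4.1 has no sample-size calculation and the shells hold placeholders. The check is whether the missing patient counts can be recovered from the printed cells.

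**Inputs.** N = 30, the maximum, from SAP 4.1 ("Up to 30 patients will be enrolled and treated with the study device"). All cell counts below are assumed for illustration.

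**Formula.** If n₁, n₂, … patients appear in several cells, the number appearing in at least one cell satisfies

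max(nᵢ) ≤ union ≤ min(N, Σnᵢ).

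The lower bound holds when the smaller sets lie inside the largest. The upper bound holds when they do not overlap, subject to the cap at N.

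| Quantity sought | Assumed cells | Sum | Possible range |
|---|---|---|---|
| Any TEAE | 18 non-serious, 9 serious | 27 (90%) | 18–27 of 30 (60%–90%) |
| Any TEAE | 24 non-serious, 9 serious | 33 (110%, impossible) | 24–30 of 30 (80%–100%) |
| Any TEAE | 27 non-serious, 6 serious | 33 (110%, impossible) | 27–30 of 30 (90%–100%) |
| Any device-related AE, one term | non-serious: 3 device only, 4 both; serious: 1 and 1 | 9 (30%) | 4–9 of 30 (13.3%–30.0%) |
| Any device-related AE, one term | 5 in one cell, 0 elsewhere | 5 (16.7%) | exactly 5 (16.7%) |

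In the first row, the non-serious table would print 18/30 = 60% against the any-TEAE label. Between 0 and 9 patients with only serious events would be missing, so the true figure could be up to 9/30 = 30 percentage points higher.

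In the fourth row, the non-serious device-only block shows 3/30 = 10%, below the whole possible range for device-related incidence.

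The sum is right only when no patient appears in more than one cell, as in the last row.

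**Event counts.** Each event has one seriousness class and one relatedness block, so the bracketed event counts do add. For example, 40 + 12 = 52 events whichever patients had them.

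**Can another table supply the counts?**

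- Within one seriousness class, the all-events block of the by-term tables pools relatedness. It gives patients per term regardless of attribution, not patients with a device-related event.
- Tables 14.3.2 and 14.3.3 have no terms and stop at 12 months. Their row for subjects with related events does not separate device from procedure. Device relationship is split into probable and possible, with no rule for a patient who has both.
- Table 14.3.8 pools one event type across seriousness, but as a rate rather than a percent of patients.

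**The case against.** The strongest case on the other side is that this is a tidy-up of shells in a small descriptive feasibility study. Several parts of it stand.

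- **Little or nothing is lost.** Listing 16.2.4 and the dataset hold every AE, and SAP 4.8.2 requires relationship and term to be listed. With at most 30 patients the counts can be derived. This limits the cost, but the reader of the tables would have to do the work that the SAP text assigns to the tables.
- **The text could be met by separate AE and SAE tables.** That is arguable for 4.8.2. It does not rescue a row labelled any TEAE in a table confined to non-serious events.
- **The any-TEAE range may be narrow here.** Protocol 10.2 expects sore throat, coughing and hemoptysis each in more than 1 in 2 patients. If they were independent with probability of at least 0.5 each (an assumption), at least 1 − 0.5³ = 87.5% of patients would have one. The 27-and-6 case above would then be more typical than the 18-and-9 case. This is fair for the 12-month any-TEAE figure. It does not help the device-related counts by term, or the post-12-month tables if these events cluster around the procedures.
- **The device-only block is plainly labelled, next to the block for both.** A careful reader would not take it for the total, but still could not work the total out.

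Stronger readings are tempting, and the documents do not support them. A reader might infer that nothing can be added; event counts can. A reader might infer that every AE table is split by seriousness; Table 14.3.8 is not. A reader might infer that device relatedness is never shown apart from procedure relatedness; Tables 14.3.2 and 14.3.3 do so at overall level. Nor do the documents say how often events will be judged both device- and procedure-related, so the size of any understatement in the device-only block is unknown.

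**Conclusion.** The point holds for patient counts. As specified, no table gives the number and percent of patients with any TEAE, or, by term, with any device-related AE. The any-TEAE row in Tables 14.3.4 and 14.3.5 omits patients whose only events were serious. The shells thus fall short of summaries that SAP 3.2.1 and 4.8.2 prespecify.

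A reader might infer that the primary safety result is compromised. It is not: SAP 4.8.1 and Table 14.3.1 give SAEs of interest by event and as a composite.

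The ranges above rest on assumed counts and N = 30. They show that the counts cannot in general be recovered, not how large the gap will be. The conclusion also assumes that the tables are programmed as titled. The correction should be made, but it is modest in consequence and would not change an endpoint.

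**What to change.** 1. Add an all-TEAE summary, serious and non-serious combined, by SOC, LLT and interval, with the same columns as the existing by-term tables. Include a row for patients with any TEAE.
2. In that summary, include *Device-related (any)* and *Procedure-related (any)* blocks. These may overlap. Each patient is counted once per row. The exclusive blocks can stay in the existing tables, where they let event counts add.
3. Relabel the overall row in Tables 14.3.4 and 14.3.5 as *Subjects with any non-serious TEAE*, and the matching row in Table 14.3.7 as any TESAEs, in line with Table 14.3.6.

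The cost is a little extra programming on the same AE dataset and one or two more tables. No new data are needed. Making the change before database lock or freeze keeps it a priori under SAP section 1.

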7 LIST OF DATA LISTINGS

No.	Title
16.2.1	Patient Disposition
16.2.2	Protocol Deviations
16.2.3	Concomitant Medications
16.2.4	Adverse events

CONFIDENTIAL:

This document and its contents are the property of Gala Therapeutics, Inc. Any use, reproduction or distribution without the written permission of Gala Therapeutics, Inc. is prohibited

	TYPE: Clinical Trial Document	Document No:	CLN-0000X
	TITLE: CS003 Statistical Analysis Plan	Revision:	A
		Release Date:	
		DCN	Page 42 of 44

Listing 16.2.2 Protocol Deviation

Site Number	Patient ID	Deviation Category	Deviation Type	Related Visit	Description of Deviation
		Major/Minor	Missed Visit	3 Months	

CONFIDENTIAL:
